Every effort will be made to follow all study subjects according to the PEACE Protocol even when they make temporary or permanent moves to another city. When a patient moves into a geographic area served by a PEACE clinical center other than the one in which the patient was originally enrolled or is currently being served, the patient will be reassigned to the care of the new center. If the patient moves into a geographic area not served by a PEACE clinical center, the patient will be placed on phone contact and the follow-up information should be obtained every six months. Resupply of medication will be mailed to the patient.

Primary outcomes will be recorded on the Outcomes Form and sent to the CSCC. For all deaths, a copy of the death certificate will be obtained. If hospitalized at the time of death, a copy of the hospital face sheet with ICD-CM code(s), or hospital discharge summary and autopsy report, if

any, will be obtained. If not hospitalized, a copy of the emergency medical services or ambulance report will be obtained. Documentation will be forwarded to the CSCC for classification by the Mortality and Morbidity Review Committee (MMRC). Two members of the committee will independently code the death as cardiovascular or non-cardiovascular.

For non-fatal myocardial infarction, a copy of the hospital face sheet with ICD-CM code(s), hospital discharge summary, cardiac enzyme laboratory report, and initial and last electrocardiograms will be obtained. Documentation will be forwarded to the CSCC for adjudication by the MMRC. Two members of the committee will independently code the event as a confirmed myocardial infarction or as not meeting the specified study criteria.

For PTCA or CABG, a copy of the hospital face sheet with ICD-CM code(s) or the hospital discharge summary will be obtained and forwarded to the CSCC.

For the primary endpoints cardiovascular death and non-fatal myocardial infarction if the adjudicators' opinions are in agreement, they constitute the final outcome determination. If the two opinions differ, a third opinion will be obtained from the MMRC Chairperson.

VI. SUBSTUDIES AND ANCILLARY STUDIES

A. Introduction

In order to derive full benefit from the data collected and to provide fair access to all study participants, the Publications and Ancillary Studies Committee (PASC) will review applications for ancillary studies, coordinate the formation of writing groups on each topic and make recommendations to the Steering Committee regarding these activities.

B. Ancillary Studies

An ancillary study will be defined as a study in which PEACE patients are used in an investigation that requires additional data not collected as part of the main protocol. Such studies may be carried out independently by PEACE investigators either as a single center or in collaboration with other PEACE investigators. Although outside funding may be sought for ancillary studies, all of these must be approved by the PEACE Publications and Ancillillary Studies Committee. This committee will assess the quality of the science proposed and determine whether conducting the ancillary study has any potential to adversely affect the main study. The contribution of the requestors of ancillary projects to the overall study will be considered. A recommendation will then be transmitted from the PASC to the Steering Committee. The Steering Committee will make the final recommendation for each report.

C. Data Storage and Analysis

Originals of each data form will be stored at the Clinical and Statistical Coordinating Center and data will be entered into their computer system. Data will be analyzed at the CSCC unless other arrangements have been recommended by the PASC and approved by the Steering Committee. All data designated as representing the PEACE study must be derived from and verified by the CSCC.

D. Application Review Process

The Publications and Ancillary Studies Committee will review proposals at each of the annual meetings as well as between meetings, if necessary. If several applications for similar studies are received, the PASC will request that the applicants resolve differences in their proposals and submit a joint application. If irreconcilable differences exist between similar applications or if the applicants cannot resolve differences or do not wish to collaborate, the PASC will individually grade the applications based upon scientific merit and feasibility, previous investigator experience, balance of projects in the overall study (to be certain that all investigators have a chance to pursue studies that they choose) and past recruitment and follow-up performances.

In order to assure that all sites have an equal opportunity to develop and participate in analyses, proposals will be circulated to each of the Principal Investigators to invite their participation. The proposer will make recommendations to the Steering Committee regarding the participants and their responsibilities in the substudy. Final decisions regarding participation rest with the Steering Committee which will receive a recommendation from the PASC.

Applications from non-PEACE investigators and institutions are welcomed but will be accorded secondary priority for approval and must be in the format that a PEACE investigator would use to make application.

All ancillary studies will be reviewed for approval by the Data and Safety Monitoring Board.

VII. PUBLICATION POLICY

The Publications and Ancillary Studies Committee will review all proposed publications and presentations and report its recommendations to the Steering Committee.

A. Data Analysis and Release of Results

The scientific integrity of the study requires that the data from all of the clinical centers be analyzed study-wide and reported as such. Thus, an individual center may not report the data collected from only that center. The development of reports of data from individual sites for the determination of institutional variability is the prerogative of the Steering Committee. Additionally, all presentations and publications are expected to protect the integrity of the major objectives of the study; data endpoints by randomization group will not be available to clinical center investigators until the completion of the study. Recommendations about the timing of presentation of such endpoint data and the meetings at which the data are presented will be discussed and approved by the Steering Committee.

B. Review Process

Each proposed manuscript, abstract, or presentation must be submitted to the Publications and Ancillary Studies Committee. The PASC may recommend changes to the authors. The PASC will make a recommendation to the Steering Committee regarding suitability of the proposed submission and the recommendation of the Steering Committee will be conveyed to the authors.

C. Primary Outcome Papers

The primary outcome papers of the PEACE trial are defined as papers that present outcome data for the entire PEACE trial (such as papers dealing with the primary and secondary endpoints). The final determination of whether a particular manuscript is a primary outcome paper rests with the Steering Committee which will receive a recommendation from the Publications and Ancillary Studies Committee.

Authorship on primary outcome manuscripts and abstracts will be "The PEACE Investigators." For such manuscripts, there will be an appendix containing the names of the organizational units and their Principal Investigators and Co-investigators. Organizational units will include the CSCC, Clinical Centers, Office of the Study Co-chairmen, and the National Heart, Lung, and Blood Institute.

D. Other PEACE Manuscripts, Abstracts and Presentations

All studies other than those designated as "primary outcome" fall into this category. The authorship of papers or abstracts resulting from these studies will name the individuals involved, ending with the phrase "for the PEACE Investigators." In addition, these manuscripts will have the same appendix as described above for primary outcome papers.

VIII. STUDY ORGANIZATION

A. Introduction

PEACE study organization includes the following components: the NHLBI, the Data and Safety Monitoring Board, the Steering Committee and its subcommittees, the Executive Committee, the Clinical and Statistical Coordinating Center, the Clinical Centers, Pharmacy Coordinating Center and the Central Biochemistry Laboratory. In the following section each component and the interrelationship among these components will be described. The organization structure that is depicted in Appendix B was developed to facilitate the conduct of the study by ensuring careful and uniform adherence to the Protocol and the Manual of Operations.

B. Structure

The Director of the National Heart, Lung and Blood Institute (NHLBI) is responsible for the use of Institute funds and the management of Institute programs. He has ultimate responsibility for the conduct of PEACE and serves as the final decision-maker for all major decisions affecting PEACE. The Institute Director appoints the Chair and members of the Data and Safety Monitoring Board (DSMB). The Principal Investigator of the NHLBI represents the Director of the NHLBI and is responsible for ensuring that the scientific and technical objectives of the study are consistent with the mission and responsibilities of the NHLBI. The Principal Investigator, or his designate, is a member of the study's Executive and Steering Committees and a voting member of each of the subcommittees (PASC and MMRC) of the Steering Committee.

1. Data and Safety Monitoring Board

The Data and Safety Monitoring Board is appointed by the Director of the NHLBI. The members are independent of the conduct of the study. They include experts in cardiology, biostatistics and bioethics. The DSMB reviews the Protocol for the main study, any proposed major modifications to the Protocol or the Manual of Operations, and the protocols for all proposed ancillary studies.

The members of the DSMB will monitor the progress of recruitment, adherence, data quality, endpoint data and side effects. Any serious event occurring during the run-in phase will be monitored by the DSMB in the same way as events occurring during the randomization phase of the trial. Summary endpoint data presented by randomization group is confidential and shared only with the DSMB. The DSMB will review reports twice a year and make its recommendations concerning the conduct of PEACE directly to the Director of the NHLBI. The Study Co-chairmen, the Principal Investigator and Co-investigators of the Clinical and Statistical Coordinating Center, and a representative of the NHLBI Project Office are ex-officio members of the DSMB.

2. Steering Committee

The Steering Committee is the representative body of study participants. The voting members of the Steering Committee include the Study Co-chairmen ([name]. and [name]., Ph.D.), the NHLBI Principal Investigator ([name].), the Clinical and Statistical Coordinating Center Principal Investigator ([name].), two clinical center Principal Investigators ([name], M.B., Ch.B., D.Phil. and [name].), and five others who will be clinical center Principal Investigators. The Co-Investigators from the CSCC will be non-voting members of the Committee. The Steering Committee provides overall scientific direction for the study through consideration of recommendations from the subcommittees. The business of the Steering Committee will be conducted in accordance with customary parliamentary procedures. The Steering Committee will meet at least once each year to review the progress of the study and to monitor non-endpoint data. The Steering Committee will not have access to endpoint data and treatment group differences until the trial is completed. The Steering Committee will establish subcommittees to support its objectives. The subcommittees are the Publications and Ancillary Studies Committee (PASC), and the Mortality and Morbidity Review Committee (MMRC). The members of the subcommittees are appointed from among the clinical

centers, CSCC, and NHLBI Principal Investigators. The chairman of each subcommittee will be a member of the Steering Committee.

All subcommittees have specific responsibilities outlined below and assume other responsibilities as requested by the Steering or Executive Committees.

- a) Publications and Ancillary Studies Committee decides on the timing and content of publications and presentations. They will review all study manuscripts prior to submission. They will review all research requests for use of study patients or accumulating study data. They will forward their recommendation for each proposal to the Steering Committee.
- b) Mortality and Morbidity Review Committee establishes classification procedures for cardiovascular and coronary heart disease mortality and definite non-fatal myocardial infarction. This subcommittee classifies endpoints on the basis of a masked review.

3. Executive Committee

The Executive Committee will consist of the Study Co-chairmen, the NHLBI Principal Investigator, and the Principal Investigator of the CSCC. In addition, the Co-investigators from the CSCC and other NHLBI investigators will be ex-officio members. They will provide study direction between meetings of the Steering Committee, develop an agenda for the annual meeting of the Steering Committee, and coordinate the activities of the two subcommittees. During the first two years, they will hold monthly conference calls or face-to-face meetings to review recruitment and patient follow-up, adherence to the Protocol with respect to drug compliance, and follow-up visit timeliness and data quality. After the recruitment phase, they will meet every six months between the annual Steering Committee meetings.

4. Clinical and Statistical Coordinating Center

The Clinical and Statistical Coordinating Center (CSCC) provides overall coordination for all aspects of the study. They participate in all aspects of the design and implementation of the PEACE trial. The Principal Investigator is a voting member of the Steering Committee and the Executive Committee. The Principal Investigator and Co-investigators provide scientific and technical service to the Steering Committee and each of its subcommittees. The CSCC has the responsibility for implementing the systems necessary for randomization, drug distribution, data collection, editing, management and statistical analyses. They are responsible for providing appropriate and timely data reports to the DSMB, the Steering Committee and its subcommittees, and the Executive Committee. The CSCC will oversee all aspects of the clinical centers' performance. They assist in the selection of the centers, train and certify the centers' staff, and coordinate the fiscal aspects of the study.

5. Clinical Centers

The clinical centers are staffed by a primary Study Coordinator and a Principal Investigator. The Principal Investigator works with the CSCC and the other members of the Executive Committee to conduct the study in accordance with the Protocol and Manual of Operations. The clinical center is expected to perform the following functions:

- a) Screen, recruit, obtain informed consent and randomize acceptable numbers of eligible patients.
- b) Dispense study medication in the manner outlined in the PEACE Protocol.
- c) Maintain contact with patients.
- d) Schedule and perform follow-up visits, submit data collection forms to the CSCC, and respond to data queries in an appropriate manner, as outlined in the protocol and the Manual of Operations.
- e) Obtain Protocol-required validating information on endpoints.
- f) Attend study meetings.

6. Knoll Pharmaceutical

Knoll Pharmaceutical Company will provide the study medication to the Pharmacy Coordinating Center (PCC). Knoll Pharmaceutical will have no access to study data prior to the termination of the trial.

7. Pharmacy Coordinating Center

The Pharmacy Coordinating Center will receive the study medication from Knoll Pharmaceutical. They will store, process and distribute the drugs to the Clinical Centers. In addition they will create, install and monitor the PEACE Trial's automated randomization and drug assignment system.

8. Central Biochemistry Laboratory

The Central Biochemistry Laboratory (CBL) will coordinate the collection, local processing and shipment of baseline blood and urine specimens from each collaborating clinic. The CBL will serve as the long term storage repository of these specimens.

REFERENCES

- 1. NCHS data calculated by National Heart, Lung, and Blood Institute, reported in The Fifth Report of the Joint National Committee on Detection, Evaluation, and Treatment of High Blood Pressure. National Institutes of Health 1993; 93-1088: 1-49.
- 2. National Center for Health Statistics. U.S. Department of Health and Human Services. Advance Report of Final Mortality Statistics, 1990. 1993; 41.
- 4. ISIS-2 (Second International Study of Infarct Survival) Collaborative Group. Randomized trial of intravenous streptokinase, oral aspirin, both, or neither among 17, 187 cases of suspected acute myocardial infarction: ISIS-2. Lancet 1988; 2:349-360.
- 5. ISIS-4 (Fourth International Study of Infarct Survival) Collaborative Group. ISIS-4: A randomized factorial trial assessing early oral captopril, oral mononitrate, and intravenous magnesium sulphate in 58,050 patients with suspected acute myocardial infarction. Lancet 1995; 345:669-685.
- Gruppo Italiano per lo Studio della Streptochinasi nell' Infarto Miocardico. (GISSI). Effectiveness of intravenous thrombolytic treatment in acute myocardial infaction. Lancet 1988; 2:349-360.

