- 6) Any of the outcomes in (5) or cardiac arrhythmias (requiring hospitalization).

In addition, the effect of trandolapril on the risk of total mortality, cause-specific mortality, as well as the individual components of the hierarchy of clinical cardiovascular events, will be estimated.

C. Patient Eligibility

The eligibility and exclusion criteria are as broad as possible to increase the generalizability of the results, while maintaining patients' safety and the scientific integrity of the trial. In attempting to be representative of the population with this disease, the trial has set a goal of including 40% women and 20% minority. Participants must meet all inclusion criteria and have none of the exclusion criteria. All potential participants with any single exclusion characteristic must be excluded. However, such patients may be reconsidered for eligibility at a later time (e.g., if a patient

had an MI less than three months prior to randomization, they may be reconsidered at a later time). However, **all** inclusion and exclusion criteria must be reevaluated at that time.

1. Inclusion Criteria

- 1) Men and women ≥ 50 years of age at the time of randomization.
- 2) Coronary artery disease documented as at least one of the following:
 - a) A documented myocardial infarction at least three months prior to randomization.
 - b) A CABG or PTCA at least three months prior to randomization.
 - c) A coronary angiogram demonstrating the presence of at least one native coronary obstruction (non-bypassed) of \geq 50% luminal diameter. The qualifying lesion(s) will be based on the most recent study.
- 3) Left ventricular function:
 - a) Ejection fraction > 40% as determined by contrast ventriculography, radionuclide ventriculography, or echocardiography performed less than 18 months prior to the date of randomization.

OR

b) A qualitatively normal echo or angiogram of the LV in the absence of wall motion abnormality. If regional dysfunction is present or the LVEF is compromised, a quantitative ejection fraction would still be required.

2. Exclusion Criteria

- 1) Potential participant is currently prescribed an ACE inhibitor which cannot be discontinued.
- 2) Contraindication to the use of an ACE inhibitor (e.g., prior adverse experience with an ACE inhibitor, current or planned pregnancy, any angioedema, or hyperkalemia).

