- 3) Current clinical condition(s) requiring the use of an ACE inhibitor (e.g., symptomatic congestive heart failure, hypertension requiring ACE inhibitor for adequate control).
- 4) Current clinical requirement for use of an angiotensin II receptor antagonist.
- 5) Hospitalization for unstable angina occurring less than two months prior to the date of randomization.
- 6) Valvular heart disease which, in the assessment of the treating physician, is likely to require surgical intervention.

- 7) Coronary artery bypass surgery within three months prior to the date of randomization.
- 8) Percutaneous transluminal coronary angioplasty within three months prior to the date of randomization.
- 9) Plans for elective coronary revascularization procedure.
- 10) Serum creatinine > 2.0 mg/dL (177 μ mol/L) (measured within 12 months prior to the date of randomization). If last serum creatinine was \geq 1.5 and \leq 2.0 mg/dL (\geq 133 and \leq 177 μ mol/L), recheck after run-in and prior to randomization. If serum creatinine > 2.0 mg/dL (177 μ mol/L) at that time, patient is excluded.
- 11) Serum potassium \geq 5.5 mEq/L (5.5 mmol/L) from most recent laboratory assessment within 12 months prior to the date of randomization.
- 12) Other concurrent medical conditions thought likely to limit five-year survival (e.g., certain cancers, cirrhosis, severe chronic obstructive pulmonary disease).
- 13) Psychosocial conditions not conducive to adherence to the long-term requirements of this trial.
- 14) Inability or unwillingness to provide written informed consent.
- 15) Women of childbearing potential not using adequate contraception.
- 16) Current use of non-FDA or non-HPB approved medication in a research trial (see Manual of Operations for details).

D. Informed Consent and Institutional Review Board (IRB)

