Each participating site will be required to submit the PEACE trial protocol to its local IRB for approval. As part of this process, an appropriate informed consent form will be developed at each site. A copy of the IRB approval letter and a copy of the consent form approved by the local IRB will be forwarded to the PEACE Clinical and Statistical Coordinating Center (CSCC). No screening, run-in visits, randomizations or study drug shipments will be allowed prior to the receipt of these documents. The consent form will, at a minimum, meet the guidelines from the Code of Federal Regulations, part 46 - Protection of Human Subjects. A sample Informed Consent Form is included as Appendix A.

E. Screening, Randomization and Follow Up

Potentially eligible and interested subjects identified through screening of outpatient clinics, coronary care units, cardiac catheterization records and other appropriate sources will be scheduled for a pre-randomization visit. At or prior to this visit the respective participant may be given the

patient brochure describing the study. Prior to the pre-randomization visit, the patient's physician will be contacted to discuss the study and the patient's potential participation. The importance of obtaining the local physician's commitment and support in maintaining long-term adherence and follow up cannot be overemphasized.

1. Pre-Randomization Visit

- a) Study requirements will be reviewed with the potential participant, and the Screening Form will be completed for eligible patients who will participate in run-in or who may be eligible based on ECG.
- b) The Informed Consent Form will be read by (or to) all eligible candidates and signed by those willing to continue. Any questions by the candidates will be addressed by the clinical staff.
- c) A baseline blood pressure will be taken and a 20-day supply of run-in trandolapril (2 mg taken once daily) with a page of instructions and possible adverse effects will be given to consenting participants.
- d) An appointment for the Randomization Visit will be made.
- e) The Screening Form will be transmitted to the CSCC.
- f) Participants whose most recent serum creatinine was ≥ 1.5 and ≤ 2.0 mg/dL, will have their serum creatinine checked after at least one week of run-in medication and before randomization. If creatinine is now > 2.0 mg/dL, the participant is ineligible and his/her primary care physician will be notified of the results.

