After oral administration, trandolapril is rapidly absorbed and converted to its active form, trandolaprilat, in the liver. Peak plasma concentrations of trandolaprilat are achieved in 4-6 hours, and steady-state in four days. Concomitant food intake did not alter trandolaprilat bioavailability. Trandolapril is excreted in the urine (33%) and bile (66%), thus dose reduction is recommended in severe renal or hepatic dysfunction. Elimination half-life of trandolaprilat is biphasic, with the prolonged terminal elimination phase being 16-24 hours.³³

In clinical trials involving more than 2200 hypertensive patients, trandolapril has been well tolerated, with an adverse effect profile similar to that of other ACE inhibitors. In a trial of 786 subjects treated with 2 or 4 mg of trandolapril for up to 12 months, cough was reported by <3%; other less frequently reported side effects included headache (1.9%), dizziness (1.8%), weakness (1.4%), palpitations (0.4%), hypotension (0.5%), nausea (0.6%), gastrointestinal disorders (0.5%), pruritis (0.4%), and rash (0.5%).³⁴

As with other ACE inhibitors, trandolapril should not be administered to pregnant or breast feeding women, to patients with a history of angioedema, or in conjunction with potassium-sparing diuretics.

B. Concomitant Medications

Study medication will be added to conventional therapy, including management of hyperlipidemia, hypertension and diabetes, as well as aspirin (unless contraindicated). Concomitant medications are recorded on the Randomization and Annual Visit Forms. Except for the recommendation of non-use of potassium-sparing diuretics, there will be no protocol restrictions on other concomitant medications.

IV. STATISTICS

A. Statistical Analysis

The primary endpoint on which the sample size determination was based is the combined incidence of non-fatal myocardial infarction, death attributed to a cardiovascular etiology, CABG or PTCA. The hypothesis of equal time to event distributions in the two treatment arms will be tested using a two-sided logrank test at the overall 0.05 (2-tail) significance level. An intention to treat analysis will be used. It is assumed that the trial will accrue patients uniformly over the first three years, with a minimum follow-up of four years.

1. Sample Size and Power

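### Potassium-sparing diuretics are ruled out with trandolapril in III.A but only discouraged in III.B; no exclusion names them, and no drug record is scheduled before active run-in or at the 4 mg visit

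*Protocol*

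**What the plan says.** **The drug section (III.A).** "trandolapril should not be administered to pregnant or breast feeding women, to patients with a history of angioedema, or in conjunction with potassium-sparing diuretics". The same section reports more hyperkalemia on trandolapril than on placebo in the earlier post-infarction trial.

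**The concomitant-drug rule (III.B).** "Except for the recommendation of non-use of potassium-sparing diuretics, there will be no protocol restrictions on other concomitant medications". On recording: "Concomitant medications are recorded on the Randomization and Annual Visit Forms". Table 1 agrees: the Current Medication row is marked at Randomization and Annual, and blank at Pre-randomization and Semi-Annual.

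**Exclusions (II.C.2).** Exclusion 2 covers contraindications to ACE inhibitors, and its examples include "current or planned pregnancy, any angioedema, or hyperkalemia". Two other exclusions name drug classes: "Potential participant is currently prescribed an ACE inhibitor which cannot be discontinued" (exclusion 1) and "Current clinical requirement for use of an angiotensin II receptor antagonist" (exclusion 4). Exclusion 11 bars a serum potassium of 5.5 mEq/L or more, on the latest value from the 12 months before randomization.

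**Dosing (II.E.1 and II.E.3).** The pre-randomization visit provides "a 20-day supply of run-in trandolapril (2 mg taken once daily"). The step to 4 mg follows at the first semi-annual visit. The only stated grounds for withholding it are a systolic pressure below 110 mmHg or symptomatic hypotension.

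**The concern.** III.A puts three situations in one sentence with one force. Pregnancy and angioedema reappear in exclusion 2. The diuretic class does not reappear in any exclusion, and III.B softens it to a recommendation. A site that follows the protocol as written can therefore enroll a user of such a diuretic, give active run-in drug and later raise the dose, although III.A advises against the combination.

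At stake are participant safety and the chance that about 160 centers handle the same patient differently. The primary comparison is not at stake.

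**Working it through.** The plan gives no figure to reproduce. The check sets the sections side by side and follows the order of visits.

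**1. Force of the rule.** III.A: the combination is to be avoided. III.B: non-use is recommended. II.C.2: 16 exclusions, none naming the class. Both sections point the same way, but only the weaker one is written as a rule for sites.

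**2. Order of events** (II.E, III.B, Table 1):

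| Visit | Trandolapril step | Current Medication marked? | Serum Potassium marked? |
|---|---|---|---|
| Pre-randomization | 2 mg active run-in dispensed | No | Yes |
| Randomization | Masked 2 mg or placebo | Yes | No |
| Month 6 | Increase to 4 mg or matching placebo | No | No |
| Month 12 | Continues | Yes | No |

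There is no scheduled drug record before the first active dose. There is one before the 4 mg step, at randomization about 6 months earlier, and none at the 4 mg visit itself.

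**3. Delay for a diuretic started between randomization and month 6.** Visits are six-monthly with a window of one month either side. The increase falls at month 6 (5 to 7) and the next drug record at month 12 (11 to 13).
- Central: 12 − 6 = 6 months after the increase.
- Shortest: 11 − 7 = 4 months.
- Longest: 13 − 5 = 8 months.

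**4. What a record would trigger.** A diuretic recorded at randomization is still not among the stated reasons to withhold the 4 mg step. The gap is therefore in the rule as well as in the recording.

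**5. Scale, by assumption only.** The documents give no prevalence of use. Suppose a share p of the 8,100 randomized (4,050 per group) use such a diuretic at entry and continue it:
- exposed to the combination during run-in: 8,100 × p
- still exposed in the trandolapril group after randomization: 4,050 × p

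| p (assumed) | Run-in | Trandolapril group |
|---|---|---|
| 1% | 81 | 40.5 |
| 2% | 162 | 81 |
| 5% | 405 | 202.5 |

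These count co-exposure, not harm. They leave out run-in participants who were never randomized. They describe users at entry and say nothing about how many start a diuretic later.

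**The case against.** The strongest reply is that III.A is drug background, III.B is the operative rule, and both advise against the combination. III.A was not written to be copied item by item into the exclusions: breast feeding stands in the same sentence and is not named there either, although the minimum age of 50 makes that nearly moot. Exclusion 2 is an open list that a site could read as covering the class.

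Table 1 also shows when drugs are written on forms, not when clinicians know about them. Exclusions 1, 3, 4 and 16 cannot be applied without asking about current drugs. The patient's physician is contacted before the pre-randomization visit. Raised potassium and creatinine are screened, and borderline creatinine is rechecked after run-in. Participants are told to report adverse events, Interim Medical History is marked at semi-annual visits, and the coordinator contacts silent participants a week after the month-6 visit. The DSMB monitors serious run-in events. Sparse recording suits a large, simple trial, the Manual of Operations may say more, and the hyperkalemia signal comes from patients with an ejection fraction of 35% or less.

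Much of this stands as mitigation. None of it names the class or makes its use a reason to withhold run-in drug or the increase. With III.B calling non-use a recommendation, a site could fairly read the combination as permitted. The Manual is not shown, and the protocol's wording would need correcting whatever it says.

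Three stronger readings are tempting but not supported:
- **That no drug record precedes the 4 mg increase.** The Randomization Form is one. Only a diuretic started after randomization escapes a scheduled record before the increase.
- **That III.A and III.B contradict each other.** They differ in force, not direction.
- **That the trial's result is compromised.** Nothing here touches the endpoint, alpha or power.

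**Conclusion.** The point holds as a mismatch in force together with a gap in a safety check. The class that III.A rules out is only discouraged in III.B and is absent from the exclusions. No drug record is scheduled before active run-in or at the 4 mg visit. Use of the class does not block the increase, and no potassium test is scheduled after pre-randomization.

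A post-randomization starter is first recorded about 6 months after the increase (4 to 8). The number of participants affected is unknown, and the table of shares is illustrative. The conclusion rests on the protocol text alone and assumes that the Manual of Operations, which is not shown, does not close the gap. The change should be made because it is cheap and protects participants; the analysis does not depend on it.

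**What to change.** 1. **II.C.2:** add exclusion 17, *Current use of a potassium-sparing diuretic which cannot be discontinued before run-in*, on the pattern of exclusion 1. Table 1 already marks Exclusion Criteria at pre-randomization, so it would be checked before run-in drug is dispensed.
2. **III.B:** replace the recommendation with *Potassium-sparing diuretics should not be used with run-in or study medication. If one becomes necessary after randomization, the dose is not increased to 4 mg, the treating physician decides whether study medication continues, and follow-up continues either way.* The absence of other drug restrictions can stay as it is.
3. **II.E.3.a:** add use of such a diuretic to the conditions that hold back the 4 mg step.
4. **Forms:** add one item, *potassium-sparing diuretic: yes/no*, to the Screening Form and to the Follow Up Visit Form of the first semi-annual visit, completed before the increase. II.E.1 already provides that "the Screening Form will be completed for eligible patients who will participate in run-in".

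**Cost.** No new visit or laboratory test is needed. Some candidates who cannot stop the diuretic are lost, and participants who start one between randomization and month 6 stay at 2 mg. The documents give no number for either group. The dose hold applies to both masked groups alike, no stop of study drug is forced, and follow-up under intention to treat is kept.

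**Limit.** The change adds no potassium monitoring, and a diuretic started after the 4 mg step is left to the treating physician's judgment.
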